### 10.4 Handling of Dropouts or Missing Data

In general, missing data will not be imputed. Summary data for observed cases only will be presented.

For weekly assessments derived from daily eCOA data, the weekly values will be considered missing if there are less than 4 days with data assessed within a week.

For the primary endpoint, overall response, subjects must have at least 4 evaluable weeks of data. An evaluable week is one in which there are at least four 24-hour daily records of abdominal pain score, number of CSBMs, and Bristol stool chart. If number of CSBMs for a date is 0, then Bristol stool chart data is expected to be missing. The day will still count towards the 4-day minimum. Subjects with less than 4 evaluable weeks of data will be considered non-responders.

Mixed model repeated measures (MMRM), which provide valid parameter estimates even with some values missing, will be used to analyze continuous assessments taken over time.

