## 11.2 Additional Analyses of the Primary Efficacy Endpoint

As a sensitivity analysis, the primary efficacy analysis of the overall response rate will be repeated for the Efficacy Evaluable Set.

The remaining additional summaries and analyses will be done using the FAS.

The overall response rate will be analyzed with the IBS subtypes combined. A CMH test stratified by subtype will be used to test for an overall difference between the treatment groups across the subtype strata. To correspond with the primary analysis, the significance level will be two-sided 0.20 and an 80% CI for the treatment difference will be provided.

The primary efficacy endpoint (overall response) will be summarized and analyzed using the same method as the primary analysis by subgroups formed by sex and by region (US, UK and Ireland). The CMH analysis of overall response stratified by subtype will also be presented by sex and by region.

The frequencies and percentages of responders and non-responders by week during the treatment period will be summarized by IBS subtype and treatment group. A summary for the subtypes combined will be included. No CIs or inferences will be given.

The overall response rate will be further analyzed using a logistic regression model for each subtype. The models will include treatment and region (US, UK and Ireland) as factors and the baseline week average of Abdominal Pain Intensity and the subtype-specific baseline value as covariates. For the IBS-D model, the baseline covariate will be the proportion (as %) of days during the consecutive week prior to baseline, used for assessment of eligibility assessment, with at least one bowel movement Type 6 or 7. For the IBS-C model, the baseline covariate will be the average stool frequency in the week prior to baseline as noted for IBS-D. Model based odds ratios will be reported with 95% CIs.

The weekly average Abdominal Pain Intensities, the Abdominal Pain Intensity differences (baseline – weekly average, such that positive differences indicate improvement), and the percent differences [ $100 * (\text{baseline} - \text{weekly average}) / \text{baseline}$ ] will be summarized by IBS subtype (including combined), treatment group, and week across the treatment period and follow-up.

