The weekly average Abdominal Pain Intensity differences during the treatment period (not including follow-up) will be further analyzed using linear models for repeated measures. The models will include treatment, region, and week as main effects, treatment-by-week as an interaction term, and the baseline week Abdominal Pain Intensity as a covariate. Separate models will be built for each IBS subtype and for the subtypes combined. The IBS subtype will be included in the model for combined subtypes as a fixed effect. The covariance matrix will be unstructured. If there are convergence issues, corrected AIC will be used to

choose between the following covariance structures: Toeplitz, heterogeneous autoregressive (1) [ARH(1)] and autoregressive(1) [AR(1)]. The method of Kenward and Roger will be used to estimate denominator degrees of freedom.

Least squares (LS) means and their standard errors (SE) from the MMRM models for the weekly average Abdominal Pain Intensity differences by IBS subtype, treatment group, and week with 95% CIs will be presented. The LSM and SE of the treatment differences from placebo will also be presented with 95% CIs and p-values from t-tests for a difference from 0.

Listings of daily assessments from the eCOA data will not be provided. However, the derived weekly endpoints and response rates will be listed by IBS subtype and treatment group.

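### The supportive weekly pain model holds the baseline slope constant over all 8 weeks; adding baseline-by-week costs almost nothing and may sharpen the later weeks

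*SAP*

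**What the plan says.** The model is one of the additional analyses in SAP 11.2. Weekly pain "differences during the treatment period (not including follow-up) will be further analyzed using linear models for repeated measures". The outcome is the drop from baseline, defined "such that positive differences indicate improvement". Region, treatment and week are the main effects, and the list of fixed effects closes with "treatment-by-week as an interaction term, and the baseline week Abdominal Pain Intensity as a covariate". No baseline-by-week term appears there or elsewhere in the protocol or SAP.

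On the residuals, "The covariance matrix will be unstructured", with Toeplitz, ARH(1) or AR(1) only if convergence fails. Least squares means are given "by IBS subtype, treatment group, and week with 95% CIs will be presented", and treatment differences from placebo carry 95% CIs and p-values. No week is named as the key one. SAP 10.4 describes these models as ones "which provide valid parameter estimates even with some values missing, will be used to analyze continuous assessments taken over time".

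The primary analysis is separate: the unadjusted Yates-corrected chi-square test of overall response (SAP 10.3 and 11.1).

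**The concern.** The plan lets the treatment effect and the covariance differ freely by week but holds the baseline slope fixed. Under SAP 10.2, baseline is the same daily pain series averaged over the 7 days before Day 1, so it acts as a week 0. If correlation decays with time, as it does in two of the three fallback covariances (ARH(1) and AR(1)), baseline predicts Week 1 better than Week 8. The slope then falls over the weeks unless growing SDs offset it. A common slope would be pulled towards the early weeks, and the misfit at later weeks would go into their residual variance. At stake is some width in the week-specific confidence intervals, recoverable from data already collected.

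**Working it through.** **The plan's own figure.** The only stated power is for the responder test: at least 80% with 125 per arm, 40% against 55%, one-sided 10%. With the continuity correction 1/125 = 0.008, null SE √(2 × 0.475 × 0.525/125) = 0.0632 and alternative SE √((0.24 + 0.2475)/125) = 0.0625, power is Φ[(0.15 − 0.008 − 1.2816 × 0.0632)/0.0625] = 83.6%. Exact enumeration gives 82.5%. The claim holds, and it does not involve the pain model, for which no SD, correlation or power is given.

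**Formula.** Set the baseline SD to 1. Let ρ(d) be the correlation at a lag of d weeks, with baseline as week 0, and s_w the weekly SD.

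- Slope of weekly pain on baseline: β_w = ρ(w) × s_w. For the change score it is 1 − β_w, so distances between slopes are the same.
- Residual covariance with a slope per week: S, with S_ww = s_w² − β_w².
- Common slope under an unstructured covariance: b = 1'S⁻¹β / 1'S⁻¹1. Replacing S by the misfit-inflated covariance leaves b unchanged.
- Variance inflation of the week-w treatment difference: 1 + (β_w − b)²/S_ww.

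**One case in full.** Take ρ(d) = 0.4 + 0.55 × 0.85^d.

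- Equal SDs: the slope is 0.868 at Week 1 and 0.550 at Week 8, and b = 0.797. S_88 = 1 − 0.550² = 0.698. Inflation is 1 + 0.0613/0.698 = 1.088. By week the ratio is lowest at Week 2 (1.00) and then rises: 1.057, 1.073 and 1.088 at Weeks 6, 7 and 8.
- Weekly SD rising linearly from 1.1 to 1.4: β_8 = 1.4 × 0.550 = 0.770 and b = 0.928. S_88 = 1.96 − 0.593 = 1.367. Inflation is 1 + 0.0251/1.367 = 1.018.

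**Week 8 variance ratio, common slope against a slope per week (all correlations and SDs assumed):**

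| ρ(d) | ρ at Week 1 → Week 8 | Equal SDs | SD 1.1 → 1.4 |
|---|---|---|---|
| 0.4 + 0.55 × 0.85^d | 0.87 → 0.55 | 1.088 | 1.018 |
| 0.5 + 0.4 × 0.8^d | 0.82 → 0.57 | 1.044 | 1.005 |
| 0.3 + 0.6 × 0.8^d | 0.78 → 0.40 | 1.079 | 1.032 |
| AR(1), 0.9 | 0.90 → 0.43 | 1.207 | 1.083 |
| AR(1), 0.85 | 0.85 → 0.27 | 1.230 | 1.131 |
| constant 0.6 | 0.60 → 0.60 | 1.000 | 1.012 |

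The last row shows that what matters is the slope, not the correlation alone. With equal SDs the slopes are equal and nothing is lost. With growing SDs they differ slightly.

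**Simulation.** 250 subjects per cohort and a true Week 8 effect of 0.30, with 1,500 complete-data runs and 600 runs with dropout missing at random (84% completers) per scenario. Entries are the empirical SD of the Week 8 estimate, common slope divided by slope per week.

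| Baseline correlation | Complete | With dropout |
|---|---|---|
| equal slopes | 1.00 | 1.00 |
| 0.7 → 0.5 | 1.02 | 1.00 |
| 0.7 → 0.4 | 1.04 | 1.04 |
| AR(1) 0.9 | 1.09 | 1.09 |

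Mean estimates were 0.294 to 0.307 under both models in every scenario. Model standard errors matched the empirical SDs within about 4%. With equal slopes the extra term moved the model SE from 0.1012 to 0.1014, or 0.2%; in variance the bound is about 1/246 = 0.4%.

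**In power terms.** For a hypothetical contrast with 80% power at two-sided 0.05, power becomes Φ(2.802/√ratio − 1.960). That is 78.4% at a ratio of 1.04, 76.9% at 1.08 and 72.5% at 1.20.

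**The case against.** The strongest reply is that this is a valid, supportive model and no decision hangs on it. It has no stated power, and a loss exists only if the slopes differ, which no figure in the documents shows. Protocol 5.1 truncates baseline pain at above 3.0 while later scores are free to spread, so weekly SDs may well exceed the baseline SD. That offsets falling correlations and can bring the loss to 0.5-3% of variance. All of this stands, and it sets the priority. It does not argue against a term that costs about 0.2% of the standard error at worst.

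Four stronger readings are tempting, and the documents do not support them.

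- **Bias under dropout.** A reader might infer that the single slope undermines the missing-data statement in SAP 10.4. The simulation with dropout missing at random found no bias, and the unstructured covariance absorbs the misfit, so the standard errors stay honest.
- **Damage where the effect is read.** A reader might place the result at Weeks 6-8. SAP 11.2 reports every week and names none, and overall response counts improved weeks anywhere in the treatment period.
- **The only inference on pain.** None other is visible, but the exploratory sections are redacted, so this cannot be confirmed.
- **A subtype-by-week term in the combined model.** No defect was shown and no gain was quantified.

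**Conclusion.** The point holds as a conditional loss of precision in a supportive analysis. The common slope is a fact of the SAP text; unequal true slopes are an assumption. Week 8 variance inflation is 0% with equal slopes, about 0.5-9% for the mixed correlation structures and about 8-23% for pure AR(1) decay. In standard error these are roughly 0.2-4% and 4-11%. The weeks affected are those furthest from the common slope, which under a decline are usually the late ones.

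The calculations omit region, and the Toeplitz, ARH(1) and AR(1) fallbacks were not examined. The planned estimates and intervals are valid as they stand.

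**What to change.** In SAP 11.2, list the pain model's terms as treatment, region, week, treatment-by-week, baseline pain and baseline-by-week.

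The cost is one sentence, 7 extra parameters per cohort model (8 slopes instead of 1) and no new data, with about 0.2% on the standard error if the slopes turn out equal. Do it before unblinding, because SAP 6 classes anything run after the blind is broken as post hoc. Low priority.

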### 11.3 Secondary Efficacy Analyses

#### 11.3.1 Global Subject Assessment of Relief

The Global Subject Assessment of Relief will be summarized with frequencies and percentages of subjects reporting each category by IBS subtype (including combined), treatment group within subtype, and windowed week. Missing values will not be reported so the denominator for percentages will be the number of subjects with a response for the week in the subtype/treatment group. No statistical inferences will be made.

Data will be listed by windowed week, including responses not windowed.

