1 SYNOPSIS

TITLE OF STUDY:

A multicentre Phase 2, randomised, double blind, placebo-controlled, parallel group study to evaluate the safety and efficacy of repeated oral doses of Blautix[™] in adult subjects with irritable bowel syndrome (IBS), subtypes IBS-C and IBS-D

NAME OF SPONSOR: 4D Pharma Plc

Phase 2

Protocol Number: BHT-II-002

Clinical Phase:

Objectives and Endpoints:

The objectives of the study are:

Primary Objective

To assess the efficacy of repeated twice daily doses of Blautix[™] >1x10¹⁰MPN for 8 weeks in adult subjects with either IBS-C or IBS-D

Secondary Objectives

To assess the safety of repeated twice daily doses of Blautix[™] >1x10¹⁰MPN for 8 weeks in adult subjects with either IBS-C or IBS-D

Exploratory Objective

CCI

The endpoints of the study are:

Primary Efficacy Endpoint

The primary efficacy endpoint is whether or not the subject is an overall responder.

A subject is an 'overall responder' if they have reported an improvement in their weekly (Cohort specific) symptoms (abdominal pain intensity and stool frequency or consistency) for \geq 50% of the treatment period (in this case 4 out of 8 weeks).

Secondary Efficacy Endpoints

Subject global assessment of relief

Stool consistency (Cohort C) /Stool frequency (Cohort D)

IBS-QOL

IBS-SSS

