5.1 Inclusion Criteria

All subjects must meet all the following inclusion criteria:

- 1. Written consent on an Institutional Review Board (IRB)/ Independent Ethics Committee (IEC) approved ICF before any study specific evaluation
- 2. Males and Females between 18 and 70 years of age
- 3. Body Mass Index (BMI): 18-39 kg/m²
- 4. Having IBS-C or IBS-D as defined by Rome IV, including Subtype Classification as defined per Table 2

Recurrent abdominal pain on average, at least 1 day/week in the last 3 months associated with two or more of the following criteria:

• Related to defecation

- Associated with a change in frequency of stool
- Associated with a change in form (appearance) of stool

The above criteria must be met for the last 3 months with symptom onset at least 6 months prior to diagnosis.

IBS-C and IBS-D subtypes will be further classified as follows:

Table 3:

IBS-C	IBS-D
□ Abdominal Pain Intensity: weekly average of worst daily (in past 24 hours) abdominal pain score of > 3.0 on a 0 to 10-point scale	\Box Abdominal Pain Intensity: weekly average of worst daily (in past 24 hours) abdominal pain score of > 3.0 on a 0 to 10-point scale
	And
And	
□ Stool Frequency: more than 25% of bowel movements with a consistency of Type 1 or Type 2 Bristol stool chart and less than 25% of bowel movements with Bristol stool form Type 6 or Type 7. Subject must have fewer than 3 CSBMs ¹ within a one week period (7 days)	□ Stool Consistency: more than 25% of bowel movements with a consistency of Type 6 or Type 7 Bristol stool chart and less than 25% of bowel movements with Bristol stool form Type 1 or Type 2. Subjects must have at least one Type 6 or Type 7 bowel movements on at least four days within a one week period (7 days).

*Stool types based on Bristol Stool Chart; Hard stools -Type 1 and 2; Soft stools – Type 6 and 7 (see Appendix 3). Source: (https://irritablebowelsyndrome.net/clinical/new-rome-iv-diagnostic-criteria/) (see Appendix 6) ¹ CSBM defined as a bowel movement that is both complete and spontaneous. Bowel movements where laxative use is recorded in the concomitant medication questions in a 24 hour period, by IBS-C subjects will not be counted as CSBMs when subtyping for randomisation.

- Have a moderate or severe IBS symptom severity score ; ≥175 at the screening visit as defined by IBS-SSS. A tolerance of -10% (≥ an IBS-SSS score of 157.5) will be allowable at the Baseline (Visit 1).
- 5.2 Exclusion Criteria

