Subjects will be asked to complete a quality of life questionnaire consisting of 34 questions with a five-point response. The individual responses to the 34 items are summed and averaged for a total score and then transformed to a 0-100 scale for ease of interpretation with higher scores indicating better IBS specific quality of life. Once subjects are randomised they will be asked to record their score on their smartphone at each clinic visit or within 24hrs prior to the Clinic Visit.

Hospital Anxiety and Depression Score (HADS) (Appendix 2)

Subjects will be asked to complete HADS which is a 14-item scale that generates ordinal data. Seven of the items relate to anxiety and 7 relate to depression. Each item is scored from 0-3 so a subject can score 0 to 21 for either anxiety or depression. Once subjects are randomised they will be asked to complete this questionnaire on their smartphone at each clinic visit or within 24hrs prior to the Clinic Visit.

Bristol Stool Chart

Subjects will be asked to record stool frequency and consistency. Stool types will be based on the Bristol Stool Chart (Appendix 3). This data will be recorded daily for a 7-day period up to Baseline (Visit 1) to allow Subject to be classified into Cohorts of IBS sub-types. Once subjects are randomised they will be asked to record their stool frequency daily up to 10 bowel movements per day and score each stool type on their smartphone. No bowel movements in any given day will also be recorded.

Stool frequency will be defined as a sum of weekly CSBMs. Stool frequency will be recorded using the following question: "How many times did you open your bowels during the past 24 hours? If you have not had any bowel movements today, please enter 0." Subjects will be reminded to rate all of their bowel movements in the Bristol Stool Chart before answering the question. CSBMs will be determined by absence of laxative use recorded in concomitant medication questions for the same 24 hour period.

IBS Symptom Severity Score (SSS) (Appendix 4)

Subjects will be asked to complete a questionnaire on severity of abdominal distension, severity of abdominal pain, frequency of abdominal pain, dissatisfaction with bowel habits, and interference of IBS symptoms with daily life. A score ranging from 0 (no symptoms) to 500 (maximum severity) can be achieved as mild (74-174), moderate (175-299) or severe (>300) IBS symptoms.

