10.5.2 Secondary Efficacy Analysis

Primary Endpoint:

[figure not shown]
Secondary Analyses of the Primary Endpoint will include the use of baseline characteristics as covariates and analyses using the Efficacy Evaluable Analysis Set.

Secondary Efficacy Endpoints:

Secondary efficacy endpoints will be compared between the two treatment groups within each Cohort using Pearson's test with Yates's correction, the Mann Whitney test or other standard statistical tests as appropriate.

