#### 11.3.2 Stool Frequency/Consistency

The mean derived weekly stool frequencies, mean changes from baseline, and mean percent changes from baseline will be summarized by IBS subtype, treatment group, and week. No summary will be done with the combined subtypes. No statistical inferences will be made.

Percent change will be calculated as follows:

- If baseline value is 0, change from baseline \* 100
- Otherwise, change from baseline/baseline result \* 100

The number of CSMBs will be summarized by week including the changes from baseline. Since these quantities are not expected to follow a normal distribution, the median changes from baseline and median percent changes from baseline will be compared using the Mann-Whitney test.

The percentage of days each week with at least one stool with a consistency of 6 or 7 will be summarized for IBS-C and a consistency of 1 or 2 will be summarized for IBS-D using the Bristol Stool Chart.

The derived data will be listed by evaluable week.

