## **13. CHANGES TO PROTOCOL SPECIFIED ANALYSES**

The EE analysis set will not be based on all major protocol deviations as indicated in the protocol, but on a subset of the major deviations that are deemed to have significant impact on efficacy data and will be determined in the data review meeting, prior to database lock and prior to unblinding the study.

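### The SAP drops the within-cohort comparison of global relief that the protocol promises and names no test for Cohort C stool consistency, and its list of changes declares neither

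*SAP*

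**What the plan says.** **Protocol.** Section 10.5.2 states: "Secondary efficacy endpoints will be compared between the two treatment groups within each Cohort". It names Pearson's test with Yates's correction, Mann-Whitney, or another standard test as suitable. Section 3.2 lists global relief, stool consistency/frequency, IBS-QOL, IBS-SSS and HADS. The synopsis divides the stool endpoint by cohort ("Stool consistency (Cohort C) /Stool frequency (Cohort D"). Section 7.1 adds: "Stool frequency will be defined as a sum of weekly CSBMs".

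**SAP, relief.** Section 11.3.1 tabulates each response category by subtype, treatment and week among those who responded, then says "No statistical inferences will be made".

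**SAP, stool.** Section 11.3.2 handles three quantities. Mean weekly stool frequency is descriptive. For CSBM counts, changes from baseline "will be compared using the Mann-Whitney test". Consistency is only summarised: "The percentage of days each week with at least one stool with a consistency of 6 or 7 will be summarized for IBS-C", with Types 1-2 for IBS-D.

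**SAP, scales.** Sections 11.3.3 to 11.3.5 give t-tests of change from baseline at each post-baseline visit for IBS-QOL, IBS-SSS and HADS, labelled exploratory. Section 10.4 says that continuous assessments over time will be analysed by MMRM, without naming endpoints. The only MMRM specified is for weekly abdominal pain, in 11.2.

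**SAP, declared changes.** Section 13 has one entry: "The EE analysis set will not be based on all major protocol deviations as indicated in the protocol".

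**The concern.** A team that follows the SAP exactly will report the first-listed secondary endpoint as weekly frequency tables with changing denominators and no comparison, although the protocol says that there will be one. SAP 6 classes any analysis done after the blind is broken as post hoc and exploratory, so a relief test added then would carry that label. Relief is rated weekly on five levels. If the time point and the scoring are not fixed in advance, a later test could be chosen from several.

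The omission would also be hard to notice. Protocol 10.4 allows minor changes without an amendment if the study report documents them. SAP 1 promises to report deviations from the SAP, but leaving out the relief test complies with the SAP. Section 13, which exists to list changes from the protocol, is the natural place to flag it and does not.

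Cohort C stool consistency has a second problem: it is unclear what would be tested. For IBS-C the SAP summarises days with Type 6-7 stools. Protocol 5.1 requires IBS-C subjects to have more than 25% of movements of Type 1-2 and "less than 25% of bowel movements with Bristol stool form Type 6 or Type 7". The Type 6-7 and Type 1-2 labels in 11.3.2 may have been exchanged between the subtypes.

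**Working it through.** **1. The plan's own figure.** The only power statement (Protocol 10.2, SAP 5) concerns the primary endpoint: 125 per arm, 40% against 55%, one-sided 10%, Yates-corrected. Exact enumeration gives 82.5% power, so the statement of at least 80% is reproduced. The documents give no figure for the secondary endpoints.

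**2. Promised comparisons against specified tests.**

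| Endpoint | Cohort C | Cohort D |
|---|---|---|
| Global relief | no test | no test |
| Stool consistency (C) / frequency (D), synopsis split | no test | Mann-Whitney, if frequency means weekly CSBMs |
| IBS-QOL | t-test | t-test |
| IBS-SSS | t-test | t-test |
| HADS | t-test | t-test |

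- Synopsis split: 5 endpoints × 2 cohorts = 10 comparisons, and 2 + 1 = 3 have no test.
- Section 3.2 read as both stool measures in both cohorts: 6 × 2 = 12 comparisons, and relief (2) + consistency (2) = 4 have no test.

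For contrast, the three scales have 9 + 1 + 2 = 12 scores (IBS-QOL total and eight subscales, IBS-SSS, two HADS scores). With two post-baseline visits (SAP 10.1 names Weeks 4 and 8) this gives 12 × 2 × 2 cohorts = 48 within-cohort p-values. With follow-up included, as in the schedule, it gives 12 × 3 × 2 = 72.

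**3. Would a relief test be informative at this size?** The effect measure is θ = P(more relief on Blautix) + ½ P(tie), with no effect at 0.50. Noether's formula at two-sided 0.05 (the SAP 6 default), 80% power and equal arms is θ = 0.5 + 2.802 × √(t / (3N)). Here N is the total rated and t = 1 − Σp³ corrects for ties. The category distributions are assumptions.

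- N = 250, ties ignored (t = 1): 0.5 + 2.802 × √(1/750) = 0.602.
- N = 250, five equal categories (t = 0.96): 0.600.
- N = 250, 10/35/35/15/5% (t = 0.91): 0.598.
- N = 200 (20% unrated, assumed): 0.614 ignoring ties, 0.609 with t = 0.91.

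Under these two distributions θ = 0.602 corresponds to a proportional odds ratio of 1.91 and 1.97. The test is feasible but would detect only a fairly large effect.

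**4. Scales: what baseline adjustment could gain.** Let r be the correlation between baseline and follow-up and k the ratio of follow-up SD to baseline SD. The documents give neither. The variance of the adjusted comparison relative to the change-score comparison is k²(1 − r²) / (1 + k² − 2rk).

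| k | r = 0.3 | r = 0.5 | r = 0.7 |
|---|---|---|---|
| 0.8 | 0.502 | 0.571 | 0.628 |
| 1.0 | 0.650 | 0.750 | 0.850 |
| 1.25 | 0.784 | 0.893 | 0.981 |
| 1.5 | 0.871 | 0.964 | 0.998 |

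With 125 per arm the change-score t-test has 80% power at 2.802 × √(2/125) = 0.354 change-score SDs. Multiplying by √0.502 gives 0.251, and by √0.998 gives 0.354. Over this assumed grid the gain runs from substantial to nothing.

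**The case against.** The best defence is that these are secondary endpoints in a Phase 2 trial without multiplicity control, that Protocol 10.4 sends minor changes to the study report, and that no document obliges SAP 13 to list this one. Protocol 10.5.2 itself names the comparison and candidate tests, so a later relief test would not be wholly unplanned. This limits the severity. It does not remove the conflict: the protocol leaves open which test is appropriate, not whether there is one, and the SAP rules inference on relief out.

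The case on stool consistency is weaker than on relief. The sentence excluding inference in 11.3.2 belongs to mean stool frequency. For consistency no test is named, and the table specifications are in a separate document. So no test specified is what the text supports.

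Four stronger readings are tempting and should be resisted:

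- *Cohort D stool frequency is untested too.* SAP 11.3.2 does treat stool frequency apart from CSBMs, but Protocol 7.1 defines stool frequency as weekly CSBMs, and those are tested.
- *The t-tests breach the protocol.* Protocol 10.5.2 permits standard tests, these are labelled exploratory, and specific sections can be read as overriding the general MMRM sentence.
- *The t-tests discard subjects with only one on-treatment visit.* A per-visit test uses every subject with a baseline and that visit. Only borrowing across visits is lost.
- *Adjustment would certainly sharpen the scale results.* The grid above shows that the gain can be nil.

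**Conclusion.** The concern holds. The SAP removes the promised comparison of global relief in both cohorts and specifies none for Cohort C stool consistency, and Section 13 is silent on both. The count is 3 of 10 under the synopsis split with frequency read as CSBMs, or 4 of 12 if both stool measures apply in both cohorts. The conflict itself rests on the text alone. The relief power figures rest on assumed response distributions and show only that a test would be feasible.

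The MMRM wording is a lesser internal inconsistency. The t-tests are valid, and what is lost is precision and borrowing across visits, by an amount that cannot be fixed from the documents and may be small.

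This should be corrected, but it does not threaten the trial: the primary analysis is untouched.

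**What to change.** 1. **Relief (SAP 11.3.1).** Before database lock and unblinding, add a within-cohort Mann-Whitney comparison of the 5-point rating in the FAS at one time point. The last on-treatment rating in Weeks 7-8 is suitable, since the End of Treatment visit may be up to 7 days early. Describe it in those words, because a Week 7 rating can then stand in for Week 8. Report the number missing per arm, test at two-sided 0.05, and label the result secondary and unadjusted for multiplicity.
2. **Stool consistency (SAP 11.3.2).** Check whether the Type 6-7 and Type 1-2 labels are swapped between subtypes, state which types define the Cohort C endpoint, and add the same kind of test. State that Cohort D stool frequency means weekly CSBMs.
3. **Interim.** SAP 10.5 puts the primary analysis, its additional analyses and the stool tables into an unblinded interim. If that has been run, label both the relief and the stool tests as added after it.
4. **SAP 13.** List any secondary endpoint that stays descriptive.
5. **Scales.** Either add a baseline-adjusted model in the 11.2 form (treatment, region, visit, treatment-by-visit, baseline score), reporting the Week 8 difference with a 95% CI, or restrict the 10.4 MMRM sentence to abdominal pain.

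The cost is SAP wording, three added tests, and at most an adaptation of the 11.2 model code. The downside is a few more unadjusted p-values. No new data are needed.
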